## 10.2. Devices and reference devices

Reference devices for the marginal bone remodelling are single tooth x-rays. These will be performed immediately after implant placement and 3-4 months after implant placement as a standard procedure in all kinds of implant placements. X-rays are a fast and common way to acquire information about the periimplant bone height. Nevertheless there might be limitations of this technique due to its two-dimensional character, its diffractions and possible distortions. As this is a standard procedure the exposure remains the same.

The device for the determination of the marginal bone remodelling is a digital impression using already said devices: scan bodies, intra-oral camera, and software. Other devices that will be used in the study are:

Periotest (Medizintechnik Gulden) and Ostell ISQ measurement (Ostell AB) will be used as a source of excitation force to acquire the impact response of the implant.

Medication that will be used in our study includes common painkillers and antibiotics.

### **10.3. Test persons**

#### **10.3.1 Inclusion Criteria:**

Patients fulfilling all of the following inclusion criteria may be enrolled in the study:

- capability of giving an informed consent
- good health as defined by the subjects medical history (no contraindications as described in the exclusion criteria below)
- age 20 to 80 years
- Patients who require 6 implants in the positions 32, 33, 34, 42, 43, 44
- edentulous mandible with enough interforaminal bone volume for placement of 6 implants
- Residual vertical bone height of at least 8mm in the interforaminal region
- Patients who wish an implant-supported restoration with six implants

#### **10.3.2 Exclusion Criteria:**

The presence of any one of the following exclusion criteria will lead to exclusion of the subject:

- Homelessness
- Smoking
- Medication with a contraindication for implant therapy
- Skeletal immaturity
- Any active malignancy or ongoing treatment for malignancy
- An active infection at the operative site

- Persistent compartment syndrome or neurovascular residua of compartment syndrome
- Pathological fractures such as those observed in (but not limited to) Paget's disease or in metastatic bone
- Contraindications to the class of devices under study, e.g. known hypersensitivity or allergy to class of devices
- Pregnancy
- Intention to become pregnant during the course of the study
- Breast feeding
- Lack of safe contraception
- Medication for anticoagulation with INR > 2
- Patients with an elevated bleeding risk

Participation in this study is performed for patients on a voluntary basis. The patients give consent to the use and interpretation of the resulting data.

The therapy-related risks of implant surgery are equivalent in all individuals. There are only standard therapy-related costs for the patients.

Individual patient identification numbers are assigned according to the time of entry into the study. On termination of a patient from the study another participants must be included so that the minimal number of participants does not fall below 20.

#### **10.3.3 Patient numbers:**

All patients who meet the study inclusion criteria will be given a unique study identification number (patient ID).

#### **10.3.4 Criteria and procedures for the withdrawal of test persons or termination of the trial.**

##### **Termination of the trial for a proband (drop-out):**

The following events lead to a withdrawal of a study participant after the initial inclusion to the investigation:

1. Finding of an incorrect inclusion during the study integration of the trial subject
2. Exitus before the last visit

3. No participation at the last visit within the prescribed time frame
4. Failure to meet the mandatory protocol requirements
5. Failure to collect at least one of the specified parameters and tests at any time of investigation
6. Deviations from the intended time periods
7. Incorrect test participant selection
8. Withdrawing consent for study participation by the candidates

When a subject withdraws after implant placement and the second surgery for the exposure of the remaining implants, the subject will be withdrawn from the study and replaced. The patient will have a final physical examination by the investigator. The obtained data of all withdrawn subjects will be analyzed.

The reasons for the withdrawal of a subject must be recorded in the log. The study is continuing with the next participant's identification number.

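### Section 10.3.4 makes a timing departure a ground for withdrawal with replacement, while the bar is due within 72 hours in the schedule and within 7 days in section 10.1

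*Protocol*

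**What the plan says.** The drop-out part of section 10.3.4 opens with "The following events lead to a withdrawal of a study participant after the initial inclusion to the investigation". Criterion 6 is "Deviations from the intended time periods". It names no visit, tolerance or test of relevance. Criterion 3, "No participation at the last visit within the prescribed time frame", has a timing element, and criterion 4, "Failure to meet the mandatory protocol requirements", could be read to include timing.

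The consequences are spread over several sections:

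- Section 10.3.4 says of a subject who leaves around the two surgeries that "the subject will be withdrawn from the study and replaced". It adds "The patient will have a final physical examination by the investigator" and "The obtained data of all withdrawn subjects will be analyzed".
- Section 10.3.2 says of any termination that "another participants must be included so that the minimal number of participants does not fall below 20". Section 11.2 also has drop-outs replaced.
- Section 11.5 requires every deviation to be reported and explained. It provides for continued follow-up after discontinuation only where the cause is safety or lack of effectiveness.

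The bar on implants 33 and 43 is due at most 72 hours after placement under Visit 3 (section 10.4) and in the Study Schedule (section 11). Section 10.1 gives a period of 7 days. The Visit 4 heading, for the visit at about day 7, again mentions fitting the bars, although the text below it does not.

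**The concern.** A late visit is an ordinary event in a surgical study with many visits. The protocol treats it in two incompatible ways: as a deviation to be logged (11.5) and as a drop-out (10.3.4). For the bar, the reader cannot even tell what counts as late.

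At stake is outcome data from patients who have already had six implants placed under the study's three healing protocols. The planned mixed model (11.2) needs a bone level at 4 months, and the main source of that value is the second surface scan. A patient withdrawn in week 1 is promised only a final physical examination. Analysing the data already obtained does not help if the second scan is never made.

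**Working it through.** **1. Bar limits side by side**

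| Place in the protocol | Timing of the bar |
|---|---|
| 10.4, Visit 3 | at most 72 h after placement |
| 11, Study Schedule | Visit 3 at most 72 h; bar fitting marked at Visit 3 |
| 10.1 | 7 days, tied loosely to manufacturing |
| 10.4, Visit 4 heading | bars named at about day 7; no bar step in the text |
| 8.6 | prosthesis attached at one week, stated as a patient benefit |

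Only the first three rows set a limit. In hours, 7 × 24 = 168, and 168 − 72 = 96. A bar fitted in that 96-hour gap complies with 10.1 and breaches Visit 3 and the schedule. Under criterion 6 the patient stays or is withdrawn depending on which section is read.

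**2. Opportunities for a timing departure before re-entry.** The schedule gives timings to Visits 3, 4, 5, 6 and 7, which is five visits between implant surgery and Visit 8.

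**3. What follows withdrawal before re-entry.** Implants 34 and 44 would still be uncovered as part of treatment. However, section 8.4 names the extension to a full-thickness flap as the added risk of taking part, and section 11 classes the intraoral scans as study-specific. No section provides for either after withdrawal.

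**4. Loss per withdrawn patient.** Planned implants: 20 × 6 = 120. Share lost: 6/120 = 5%. Per healing protocol: 20 × 2 = 40 implants, of which 2/40 = 5% are lost.

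**5. Extra enrolments.** The protocol gives no deviation rate, so the proportion p of patients withdrawn for timing before the second scan is assumed. Patients needed for 20 with a second scan = 20/(1 − p):

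- p = 5%: 20/0.95 = 21.1, about 1 extra
- p = 10%: 20/0.90 = 22.2, about 2 extra
- p = 20%: 20/0.80 = 25.0, 5 extra

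**6. Scan timing.** The second scan is at 3–4 months in the synopsis and 10.1, with matching x-ray and stability times in 10.2 and the clinical evaluation list. It is at four months under Visits 5–7 and in the scan analysis, and at 4 months ±7 days in the schedule. A re-entry at exactly 3 months meets the wider range and misses the narrower one. By then the scan has been made, so its data are analysed. All six implants are scanned together, and section 10.1 expects a steady state after three months. This conflict alone does little harm.

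**7. Sample size.** The stated 8 per group (t-test) and 9 per group (analysis of variance) both reproduce, at 81% power each. Neither depends on this point.

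**The case against.** The strongest case on the other side is that this is loose drafting in an exploratory pilot. Visit 3 and the schedule agree on 72 hours, the wording in 10.1 can be read as manufacturing time, and the Visit 4 heading looks like a leftover. Most visits have tolerances, so the natural meaning of criterion 6 is a visit outside its window, not any lateness. Withdrawing late-loaded patients also protects the meaning of immediate loading.

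Much of this stands, and it limits the point. Several stronger readings are tempting but unsupported:

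- **Section 8.6 as another bar limit.** It describes a benefit, and a bar fitted by 72 hours satisfies it.
- **Loss of all bone-level data.** Section 10.2 calls the 3–4 month single-tooth x-ray standard care, and section 11.3 uses x-rays as well as scans for crestal bone level. A radiographic change may still exist. What has no provision is the scan-based change.
- **Extra implant operations caused by replacement.** Under 10.3.5, eligible patients had already chosen six implants independently of the study. The added burden is the study-specific procedures and the extended flap.
- **Loss of power or imbalance between protocols.** Replacement holds the number at 20, and each loss removes two implants from every healing protocol.
- **Section 10.3.4 alone as the basis for replacement in week 1.** Its sentence refers to withdrawal after implant placement and the second surgery. That may be meant as the interval between them, but it does not say so. Replacement rests on 10.3.2 and 11.2.

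The objection does not remove the rule itself. The list is worded as leading to withdrawal, with no discretion, and 7 days in 10.1 is still a stated period. Agreeing on 72 hours would still leave a bar fitted at 73 hours as a ground for withdrawal.

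**Conclusion.** The point holds and is minor. Criterion 6 turns a scheduling departure into withdrawal with replacement, in conflict with the deviation route in 11.5, and the bar limit it would be applied to differs by 96 hours between sections. Each patient withdrawn for timing before re-entry costs the scan-based outcome for six implants (5% of the planned total and of each healing protocol) and brings one further enrolment. The total depends on a deviation rate that the protocol does not give. At assumed rates of 5% to 20% it is 1 to 5 extra patients.

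This assumes that the criterion is applied as written and that no second scan is made after withdrawal. If investigators kept such patients regardless, no data would be lost, but they would be departing from the text.

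**What to change.** Delete criterion 6 and the timing part of criterion 3 in section 10.3.4. State that neither a timing departure (criterion 4) nor a single missed parameter (criterion 5) is a reason for withdrawal. Criterion 5 has to be included, because otherwise a late patient who misses one measurement would still be withdrawn. Suggested rule:

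- A departure from a scheduled time is recorded as a deviation under 11.5, with the actual hours from insertion to bar and days from insertion to second scan.
- The patient is kept, has the second scan, is analysed and is not replaced.

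Use at most 72 hours for the bar and 4 months ±7 days for the second scan throughout. This means correcting the synopsis treatment plan, 10.1, 10.2, the Visit 4 heading and the clinical evaluation list. Section 8.6 can stay.

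The downside is that some implants in the loaded group will have been loaded after 72 hours, which changes exposure in that group only. Add a sensitivity run of the mixed model without those patients.

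The cost is an amendment under 11.4 and one extra model run. Visit data are already in the medical files (11.1) and deviations must already be reported, so no new visit or type of measurement is needed.

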#### **Termination of the entire trial:**

A termination of the study may take place after consultation between the following Parties: Investigators, Ethics Committee

The investigator may cancel the study at any time for the benefit and in the interest of the participants, if severe adverse reactions or other unforeseen circumstances occur. In this case, the Ethics Committee will be informed.

#### **10.3.5 Time point of admission.**

Patients who already decided on an implant-supported superstructure with six implants independently from this study are eligible for the trial.

All patients that fulfill the inclusion criteria and want to participate at the trial will be given a patient information leaflet and will be able to give the informed consent on a separate agreement form. Admission to the trial starts at Visit 1 when the patients will be again informed about the course of the study, the procedures and examinations. There will be enough time for the patients to reconsider their entry into the trial.

#### **10.3.6 Anticipated total duration of the clinical trial.**

The anticipated total duration of the trial lasts from inclusion of 20 patients until the last measurements performed on the surface scans. We assume the completion of the trial in December 2018

### **10.3.7 Anticipated duration of the participation of each test person.**

The total duration of the participation of each test person of the trial lasts from Visit 1 to Visit 8. That is the time after the implant exposure and the second surface scan. All necessary measurements will have been performed. After the suture removal, patients will be free to proceed with further prosthetic treatment.

### **10.3.8 Required number of test persons to be included in the clinical trial.**

Based on the former study performed at our department (Lorenzoni et al. 2003) we performed a sample size estimation. A sample size of 8 in each group will have 80% power to detect a difference in means of -0,580 (the difference between a Group 1 mean,  $\mu_1$ , of -0.910 and a Group 2 mean,  $\mu_2$ , of -0.330) assuming that the common standard deviation is 0.380 using a two group t-test with a 0.05 two-sided significance level. When the sample size in each of the 3 groups is 9, a one-way analysis of variance will have 80% power to detect at the 0.05 level a difference in means characterized by a Variance of means of 0.060, assuming that the common standard deviation is 0,380.

Based on these statistical calculations and considerations on possible dropouts, a patient sample size of 20 was determined.

### **10.3.9 Estimated time required to obtain the stated number of persons (i.e., duration of recruitment).**

**10.4.** Recruitment will take place until the required number of persons is reached. We estimate 1 year to obtain the necessary number of patients. **Treatments**

#### **Visit 1: Patient recruitment and screening**

20 patients requiring an implant treatment of the edentulous lower jaw will be included in the study in compliance with the above inclusion and exclusion criteria. All patients will be recruited from the regular pool of patients seeking implant therapy at the Dental School of Medical University of Graz.

No additional efforts for recruitment will be undertaken.

. Preoperative evaluation will include a complete medical history and a clinical and radiographic oral examination of the recipient site.

All patients will be given a patient information leaflet and will be able to give the informed consent on a separate agreement form.

During the first visit, about one week prior to the planned implant surgery, the participants will be informed about the course of the study, the procedures and examinations. The patient's history will be taken and the current health status recorded. All relevant demographic, medical and dental data of the patients will be recorded and the agreement to participate in the study will be obtained. For preoperative, radiological diagnostics (evaluation of mandibular, measuring the residual bone height) a panoramic x-ray will be performed.

Additionally the patients will fill out the OHIP-G 14 questionnaire to acquire information about the oral health-related quality of life of the patients as a baseline before the study. Intraoral Photographs will be taken.

### **Randomization and Blinding**

Due to the prosthetic restoration and in order to prevent any acting forces on the neighboring implants it is not possible to perform randomization or blinding of neither the patients nor outcome assessors. The implants are always placed at the same position and the positions of the immediately loaded and non-loaded submerged and transgingival healed implants are predetermined.

### **Visit 2: Implant Surgery and first scan**

At visit 2 a preoperative digital volume tomography will be performed.

All surgical procedures will be performed on an outpatient basis under local anesthesia under standard conditions in septic surgery. All patients will be advised to rinse for at least 1 minute with 0.2% chlorhexidine digluconate. Preoperatively, the surgical site will be evaluated. After preparation of a full thickness flap the bone will be assessed for quality and quantity.

All patients will receive CE-certified implants of the same company and with the same design used in the Department of Oral Surgery & Radiology and Division of Prosthodontics, Restorative Dentistry, Periodontology and Implantology, Dental

School at Medical University of Graz as standard implants, that are approved in Austria (ASTRA TECH® Implant System, Dentsply Implants).

The implants will be placed in the interforaminal region at positions 34, 33, 32, 42, 43, 44 with a minimum distance of 3 mm between each implant shoulder (Danza et al, 2011). The upper edges of the implants will be placed at the bone level and by achieving the necessary primary stability. After the implant placement any excessive bleeding will be stopped, by applying bone wax or cauterization. The bone level in relation to the implant margin will be scanned using CEREC Omnicam (Dentsply Sirona) and appropriate scan bodies will be used on all 6 implants to acquire a fixed reference for the later comparison on all 6 implants.

Additionally conventional impressions using Transfer Abutments and Aquasil (Dentsply DeTrey) will be performed for manufacturing of the dolder bars for immediate loaded implants on positions 33 and 43, and transgingival healing abutments will be applied to the implants on positions 32, 33, 42, 43. The Implants on positions 34 and 44 will be left for submerged healing using cover screws.

Finally, the mucoperiosteal flaps will be adapted and sutured tightly. For post-operative, radiological diagnostics a panoramic x-ray and single tooth x-rays of all implants will be taken. The administration of antibiotics, anti-inflammatory or other accompanying medication will be documented. Intraoperative Photographs will be taken.

### **Visit 3: Integration of dolder bar to Implants 33 and 43**

Maximal 72 hours after the implant placement, the manufactured dolder-bar will be integrated to the implants on positions 33 and 43 and the prosthesis will be adapted to fit. The patients' perception and acceptance will be assessed using the visual analog scale (VAS (Bijur, 2008)) assessing pain and swelling occurring after implant surgery. Intraoral Photographs will be taken.

### **Visit 4: Suture removal and integration of the dolder bars**

Approximately to 7 days following the implant placement, all sutures will be removed and the patients' perception and acceptance will be assessed using the

visual analog scale (VAS) assessing pain and swelling occurring after implant surgery. Intraoral Photographs will be taken.

To evaluate the quality of life the OHIP-G 14 questionnaire will be filled out by the patients.

### **Visits 5-7: healing period**

A four-month healing period of the implants follows. Regular clinical checks will be carried out at intervals of about 4-5 weeks with sensitivity tests, patient comfort tests (VAS) and questionnaires on general patient satisfaction (oral health impact profile: OHIP-G 14, (Slade 1997)). To evaluate the quality of life the OHIP-G 14 questionnaire will be regularly filled out by the patients

### **Visit 8: Re-entry surgery and second scan**

All patients will be advised to rinse for at least 1 minute with 0.2% chlorhexidine digluconate.

In the second surgery, the exposure of the remaining implants on positions 34 and 44 will be performed by making a crestal incision. To perform the second scans the incision will be extended to a full thickness flap to evaluate the bone quality and quantity around all 6 implants. The bone level in relation to the implant margin will be scanned using CEREC Omnicam (Dentsply Sirona) and appropriate scan bodies will be used on all 6 implants to acquire a fixed reference for the later comparison on all 6 implants. Intraoperative Photographs will be taken.

One week (7 - 9 days) following implant exposure, all sutures will be removed and each patient's perception and acceptance will be assessed using visual analog scale (VAS) assessing pain and swelling occurring after implant surgery.

Subsequently to visit 7, all patients will undergo and continue their regular therapy. During this period, abutment connection, impression taking and various try-ins will take place until the insertion of the final reconstruction will be performed. Any adverse events occurring during this period will be recorded. To evaluate the quality of life the OHIP-G 14 questionnaire will be filled out by the patients

### **Visits 9-12 follow-up after implant placement**

During the follow-up time regular radiological and clinical recall checkups will be carried out. Oral hygiene and periodontal or peri-implant conditions will be controlled and documented and professional tooth cleaning (scaling, root planing) will be performed in intervals adjusted to the patients' needs.

Radiographic check-ups will be scheduled 12 and 24 months after the first surgery. Standard x-rays and panoramic x-rays will be produced and any adverse events occurring during this period recorded.

## **Study Procedures**

During the observation period, the implant survival rates will be levied, clinical and radiological controls will be carried out and the incidence of biological and technical complications will be documented. Furthermore, a questionnaire on general patient satisfaction will be completed (Oral health impact profile: OHIP-G14, (Slade 1997)).

### **1. Clinical evaluation**

- Measurement of insertion-torque after the placing of implants
- Assessment of the stability of inserted implants by determining the Periotest and ISQ values:
  1. Immediately after the insertion
  2. During the postoperative visits
  3. After exposure of the implants 3-4 months after implant placement
- Investigation of patient satisfaction using a questionnaire (OHIP-G 14 (Slade 1997))
- Evaluation of patient's perception/acceptance using a questionnaire with a scale ranging from 1 to 10, where 1 represents „no pain“ and 10 the „most painful“. The perception of pain and swelling will be assessed.
- Intra-oral photographs (frontal and profile view including a calibrated size mark) taken at determined time points at six study visits for documentation.
- Subjective assessment of the soft tissue by the study dentist according to the following four categories: normal, swollen, red, and dehiscence.
- Assessment of the extra-oral and intra-oral sensitivity by the study dentist according to two categories: regular and disturbed.

- Assessment of adverse events by the study dentist and by questioning the patient throughout the clinical examination.

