### 9.2. Primary and secondary hypotheses

Specifically, the following questions should be answered in this clinical trial:

- Are there differences in periimplant bone remodelling between the submerged, transgingival healed non-loaded implants and immediately loaded implants within the first 4 months of osseointegration?
- Are there differences in periotest or ISQ values between the submerged, transgingival healed non-loaded implants and immediately loaded implants within the first 4 months of osseointegration?
- Are there differences in survival rate between the submerged, transgingival healed non-loaded implants and immediately loaded implants within the first 4 months of osseointegration?
- Are there differences between the different measurement methods (X-rays versus Probing versus Surface Scans)

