| Photographs                           | X           | X  | x                | X            |                 |              | X           | X            |                |                |  |
| Digital Volume Tomography             |             | x  |                  |              |                 |              |             |              |                |                |  |
| Panoramic x-ray                       | X           | X  |                  |              |                 |              | X           |              |                |                |  |

|  |  |   |   |   |   |   |   |   |   |   |
|--|--|---|---|---|---|---|---|---|---|---|
| Single tooth x-ray, probing                                |  | X |   |   |   | X |   |   | x | x |
| Clinical evaluation  |  |   | X | X | X | X | X | X | X | X |
| Conventional Impressions                                   |  | X |   |   |   | X |   |   |   |   |
| Periotest / ISQ-measurement                                |  | X |   |   | X | X |   | X | X | X |
| Implant exposure 32, 42                                    |  | X |   |   |   |   |   |   |   |   |
| Implant exposure 33, 43                                    |  | X |   |   |   |   |   |   |   |   |
| Implant exposure 34, 44                                    |  |   |   |   |   | X |   |   |   |   |
| Integration of dolder bars to implants on positions 33, 43 |  |   | X |   |   |   |   |   |   |   |
| Further Treatment for definitive prosthetic therapy        |  |   |   |   |   |   | X | X | X | X |

The use of three different implant healing protocols, the OHIP-G 14 questionnaire, the pregnancy testing and the intraoral camera scans are study-specific procedures while all other procedures are routine examinations.

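### Withdrawal criterion 5, read strictly, is triggered in every patient by Periotest/ISQ readings that the covered implants 34 and 44 cannot give at Visits 5-7

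*Protocol*

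**What the plan says.** **Measurement.** Section 10.4, Study Procedures, 1. Clinical evaluation, calls for "Assessment of the stability of inserted implants by determining the Periotest and ISQ values" at three times: directly after insertion, "During the postoperative visits", and after exposure at 3-4 months. No position is exempted. In section 11, the row "Periotest / ISQ-measurement" is marked at Visits 2, 5-7, 8, 10, 11 and 12 and is not split by position.

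**Access.** At Visit 2: "The Implants on positions 34 and 44 will be left for submerged healing using cover screws". At Visit 8, "the exposure of the remaining implants on positions 34 and 44 will be performed by making a crestal incision". The schedule row "Implant exposure 34, 44" also has its mark at Visit 8.

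**Question asked.** Section 9.2 asks: "Are there differences in periotest or ISQ values between the submerged, transgingival healed non-loaded implants and immediately loaded implants", over the first 4 months. It fixes no visit.

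**Withdrawal.** Section 10.3.4 lists as item 5 of the events leading to withdrawal: "Failure to collect at least one of the specified parameters and tests at any time of investigation". The same section says that data already obtained from withdrawn subjects are analysed. Sections 10.3.2 and 11.2 require replacement so that 20 patients are kept.

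**The concern.** The plan appears to schedule a test that cannot be done on a third of the implants at three visits, and then to make a missing test a ground for withdrawal. Sites would have to guess which implants to measure at Visits 5-7 and whether an unobtainable reading counts against the patient.

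What is at stake is mainly the primary endpoint. Bone level change needs the scan at re-entry surgery, about 4 months after placement. Visits 5-7 fall at 1, 2 and 3 months. A patient withdrawn there over a secondary measurement never reaches the second scan. If sites instead set the rule aside case by case, withdrawal becomes a matter of judgement in a trial where, by its own statement, neither patients nor outcome assessors are blinded.

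**Working it through.** The plan states no number of stability readings and no power for Periotest/ISQ, so there is no figure of its own to reproduce here. The sample-size figures in 11.2 concern bone level and do not enter.

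**1. Can the reading be taken at Visits 5-7?** Section 10.1 takes the second-stage stability values after gingiva formers have been mounted, which needs an exposed implant. Implants 34 and 44 are exposed only at Visit 8. Positions 32, 33, 42 and 43 receive transgingival abutments at Visit 2 and are accessible throughout.

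**2. Count.** Inputs: 6 implants per patient and 20 patients (10.1); 2 submerged implants (Visit 2 text); stability marks up to Visit 8 at Visits 2, 5, 6, 7 and 8 (section 11). Assumption: each mark means all six implants.

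- Per patient up to Visit 8: 6 × 5 = 30 readings, of which 2 × 3 = 6 cannot be taken; 6/30 = 20%.
- Over 20 patients: 20 × 30 = 600, of which 20 × 6 = 120 cannot be taken.
- Visits 5-7 alone: 20 × 6 × 3 = 360, of which 20 × 2 × 3 = 120 cannot be taken (33%); 240 remain.
- Visits 2 and 8: 20 × 6 × 2 = 240, all obtainable, or 80 per protocol.

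**3. Patients meeting criterion 5 for this reason alone.**

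| Meaning of criterion 5 | All six implants specified at Visits 5-7 | Only accessible implants specified |
|---|---|---|
| Any single item missing | 20 of 20, and every replacement | 0 of 20 |
| Nothing collected | 0 of 20 | 0 of 20 |

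The text does not settle either axis. The adjoining items, on failing protocol requirements and on departing from the intended time periods, are equally strict, so the upper row is a natural reading.

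**4. Consequence of the upper-left cell.** The first unobtainable reading falls at Visit 5, 1 month after placement. Withdrawal then leaves the first scan but no second one, so no bone level change. The replacement meets the same rule at the same visit.

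**5. Do the passages agree on the interim visits?** No. The Clinical evaluation list refers to postoperative visits in general. The schedule marks Visits 5-7 but not 3 or 4. The text for Visits 5-7 in 10.4 lists sensitivity tests, VAS and OHIP-G 14, and no Periotest/ISQ.

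**The case against.** The strongest reply is that the comparison is already placed where it can be made. Section 10.1 takes stability values directly after insertion and names second-stage surgery as the point at which they are evaluated for differences between loaded and non-loaded implants. Section 11.3 can also be read as comparing values at insertion with values at four months. Section 11.2 plans descriptive and exploratory evaluation, and its mixed model is for bone level, so no repeated-measures stability analysis is planned that the gaps would distort. This stands. A reader might infer that the second hypothesis in 9.2 cannot be answered for the submerged protocol; the documents do not support that.

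The second reply is that nobody would count a covered implant as a failure to collect: the schedule row names no implants, and criterion 5 can mean that nothing was collected. This stands in part. It makes 20 of 20 conditional, but it does not make the rule clear.

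The third reply is that obtained data of withdrawn subjects are analysed. This also stands. A reader might infer that no patient would be left to evaluate; the text does not say so, and what was collected is kept. It does not supply the second scan, which would not have been obtained.

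**Conclusion.** The conflict between the stability schedule and the submerged healing of implants 34 and 44 is real. It affects 120 of 360 readings at Visits 5-7 if all six implants are meant. By itself this is a gap in interim readings of a secondary outcome and leaves the comparison at Visits 2 and 8 intact.

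The part that matters is criterion 5. As written, it allows withdrawal and replacement for one missing secondary test, possibly before the scan that gives the primary endpoint. All 20 patients and every replacement meet it on two assumptions: that any single missing item suffices, and that all six implants are specified at Visits 5-7. If either fails, none meets it for this reason. The primary endpoint and the sample size are touched only if the rule is applied in that strict sense. It should be corrected, because the strict sense is a natural one and the correction is cheap.

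**What to change.** 1. Reword criterion 5 in 10.3.4 so that a missing secondary measurement, or one that cannot be taken by design, is recorded as missing and does not by itself withdraw or replace the patient. This concerns study status and data recording only, not treatment.
2. In the Clinical evaluation list and in the schedule row, mark Periotest/ISQ at Visits 5-7 as applying to the accessible implants only (32, 33, 42, 43). Reconcile both with the text for Visits 5-7, which lists no such measurement.
3. State that the three-protocol stability comparison rests on Visits 2 and 8, and that any use of the interim readings is confined to the two protocols measured.

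Cost: protocol wording, through an amendment under 11.4. No measurement is added and the sample size does not change.
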